### 7.4. Immunogenicity

#### 7.4.1. Immunogenicity Analyses

The immunogenicity samples must be processed and shipped as indicated to maintain sample integrity. Any deviations from the immunogenicity processing steps, including any actions taken, must be documented and reported to the Sponsor. On a case-by-case basis, the Sponsor may make a determination as to whether sample integrity has been compromised. Any sample deemed outside of established stability, or of questionable integrity, will be considered a protocol deviation.

CCI

#### **7.4.2. Plasma for Analysis of ADA (Anti-PF-06741086) and NAb**

During all study periods, blood samples (9.0 mL) to provide approximately 3.0 mL plasma for ADA and NAb analysis will be collected into appropriately labeled tubes containing sodium citrate at times specified in the [Schedule of Activities](#).

Details regarding the collection, processing, storage and shipping of the blood samples will be provided in the central lab manual.

#### **7.4.3. Shipment of Immunogenicity Samples**

The shipment address and assay lab contact information will be provided to the investigator site prior to initiation of the study.

### **7.5. Pharmacodynamics**

#### **7.5.1. Pharmacodynamic Markers**

The PD samples must be processed and shipped as indicated to maintain sample integrity. Any deviations from the PD processing steps, including any actions taken, must be documented and reported to the Sponsor. On a case-by-case basis, the Sponsor may make a determination as to whether sample integrity has been compromised. Any sample deemed outside of established stability, or of questionable integrity, will be considered a protocol deviation.

CCI

##### **7.5.1.1. Samples for TFPI Level**

During all study periods, blood samples (2.7 mL) to provide approximately 1.0 mL plasma for TFPI level analysis will be collected into appropriately labeled tubes containing sodium citrate at times specified in the [Schedule of Activities](#).

Details regarding the collection, processing, storage and shipping of the blood samples will be provided in the central lab manual.

##### **7.5.1.2. Samples for Thrombin Generation**

During all study periods, blood samples (3.5 mL) to provide approximately 600 µL plasma for TGA analysis will be collected into appropriately labeled tubes containing sodium citrate at times specified in the [Schedule of Activities](#).

Details regarding the collection, processing, storage and shipping of the blood samples will be provided in the central lab manual.

CCI [Redacted]

CCI [Redacted]  
CCI [Redacted]

[Redacted]

[Redacted]

CCI [Redacted]

[Redacted]

[Redacted]

C  
 C  
 I

### 7.7. Blood Volume

The total blood sampling volume for individual subjects in this study is approximately 389.3 mL for SC cohorts and 428.7 mL for IV cohorts (based on Screening through Day 113). The table below reflects approximate sample volumes needed for each measured endpoint. The actual collection times of blood sampling may change, but the total blood volume collected should not increase. Additional blood samples may be taken for safety assessments at times specified by Pfizer, provided the total volume taken during the study does not exceed 550 mL during any period of 30 consecutive days.

**Table 6. Blood Volume for SC Cohorts**

Sample Type	Sample Volume (mL)	Number of Sampling Times			Total Volume (mL)
		Screening	Study Period	Follow-Up	
Safety Labs					157
Serum chemistry (with Lipid profile a )	5	1	7	1	45
Hematology	3	1	7	1	27
Prothrombin 20210 mutation	3	1	0	0	3
Factor V Leiden mutation testing	3.5	1	0	0	3.5
aPTT, PT/INR, Anti-thrombin III b , Factor VIII and Factor IX activity c , Fibrinogen, Protein C a , Protein S a , D-dimer, PF1+2 (PD samples) [Single combined sample]	4.5	1	11	1	58.5
Serology (HBs Ag, HBc Ab, HCV Ab, and HIV)	5	1	0	0	5
Cardiac Troponin I d	3	0	5	0	15
PK	4.5	0	11	1	54
Immunogenicity (ADA, NAb)	9	0	5	1	54
PD (note some PD assayed from safety samples)					106.8
TFPI level	2.7	0	11	1	32.4
TGA	3.5	0	11	1	42
dPT	2.7	0	11	1	32.4
Factor VIII and Factor IX inhibitor a	4.5	1	0	0	4.5
CCI [REDACTED]	[REDACTED]	[REDACTED]	[REDACTED]	[REDACTED]	[REDACTED]
Banked biospecimens	4	0	1	0	4
TOTAL					393.8

a at Screening only.

b at Screening and Days 1, 8, 15, 22 and 29 only.

c at Screening and Day 1 only.

d at Days 1, 8, 15, 22 and 29 only.

**Table 7. Blood Volume for IV Cohorts**

Sample Type	Sample Volume (mL)	Number of Sampling Times			Total Volume (mL)
		Screening	Study Period	Follow-Up	
Safety Labs					161.5
Serum chemistry (with Lipid profile a )	5	1	7	1	45
Hematology	3	1	7	1	27
Prothrombin 20210 mutation	3	1	0	0	3
Factor V Leiden mutation testing	3.5	1	0	0	3.5
aPTT, PT/INR, Anti-thrombin III b , Factor VIII and Factor IX activity c , Fibrinogen, Protein C a , Protein S a , D-dimer, PF1+2 (PD samples) [Single combined sample]	4.5	1	12	1	63
Serology (HBs Ag, HBc Ab, HCV Ab, and HIV)	5	1	0	0	5
Cardiac Troponin I d	3	0	5	0	15
PK	4.5	0	15	1	72
Immunogenicity (ADA, NAb)	9	0	5	1	54
PD (note some PD assayed from safety samples)					115.7
TFPI level	2.7	0	12	1	35.1
TGA	3.5	0	12	1	45.5
dPT	2.7	0	12	1	35.1
Factor VIII and Factor IX inhibitor a	4.5	1	0	0	4.5
Exploratory biomarkers	2.7	0	5	0	13.5
Banked biospecimens	4	0	1	0	4
Discard tube	2	0	4	0	8
TOTAL					433.2

a at Screening only.

b at Screening and Days 1, 8, 15, 22 and 29 only.

c at Screening and Day 1 only.

d at Days 1, 8, 15, 22 and 29 only.

### 7.8. Triggered Requirements

Condition	Action

 
• Platelet count <75,000/<math>\mu</math>L.
 
• Fibrinogen level < LLN.
 
• Hemoglobin level <10 gm/dL.
 
• PT/INR <math>\geq</math>1.25 times the ULN
 
	Subjects who are found to have one of the coagulation pathway abnormalities defined by these corresponding lab value criteria should be brought into the clinic immediately for an unscheduled visit and the respective laboratory test should be repeated.
Positive ADA	Subjects may be requested to return for additional follow-up visits after Day 113. Extended follow-up visits every 2 weeks for up to 3 months, including vital signs, immunogenicity, AE and concomitant medication assessments, may be performed.

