**Table 2. Study Flowchart – Treatment and Follow-up Period (Day 30 to Day 113)**

Protocol Activity	Treatment										Follow-up/End of Study f
	Day 30 PK/PD Blood Draw	Day 33 PK/PD Blood Draw	Day 36 (SC Cohort)	Day 43 (SC Cohort)	Day 50 (SC Cohort)	Day 57	Day 64 (SC Cohort)	Day 71 (SC Cohort)	Day 78 (SC Cohort)	Day 85	
Visit Window relative to end of Day 29 IP administration	-6 hours/+1 day	-6 hours/+1 days	±2 days	±2 days	±2 days	±2 days	±2 days	±2 days	±2 days	±2 days	±7 days
Physical examination a						X				X	X
Weight						X				X	X
Contraception instructions/check b						X				X	X
Vital Signs c						X				X	X
Urinalysis						X				X	X
Serum chemistry						X				X	X
Hematology d						X				X	X
TFPI level	X	X				X				X	X
PT/INR						X				X	X
aPTT						X				X	X
Fibrinogen						X				X	X
Thrombin Generation (TGA)	X	X				X				X	X
Prothrombin fragment 1+2 (PF1+2)	X	X				X				X	X
D-dimer	X	X				X				X	X
Dilute prothrombin time (dPT)	X	X				X				X	X
PK blood sampling	X	X				X e				X	X
Immunogenicity (ADA, NAb)						X				X	X f
CCI											
Investigational Product administration			X g	X g	X g	X	X g	X g	X g		

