### 3.3. Dose Escalation and Stopping Rules

Dose escalation stopping rules will be used to determine whether the maximum tolerated dose has been attained.

Dose escalation will not occur if 2 or more dose-limiting toxicities are met within a dosing cohort of 6 subjects. Dose escalation may occur if  $\leq 1$  dose limiting toxicity is observed within a dosing cohort of 6 subjects. Dose limiting toxicities are defined as:

- Treatment emergent laboratory abnormality as specified in [Appendix 2](#);
- Treatment emergent vital sign abnormality as specified in [Appendix 2](#);
- Treatment emergent ECG abnormality as specified in [Appendix 2](#);
- Treatment emergent severe or  $\geq$  Grade 3 adverse event, as graded by the NIAID DMID criteria for severity unless incontrovertibly due to extraneous causes.

Additional rules governing dose escalation are as follows:

- Dosing at the current dose level (or higher dose levels) will be suspended for any treatment emergent thrombotic event (see [Appendix 1](#) for qualifying AEs) in a subject receiving PF-06741086 to permit characterization of the respective event and communication to regulatory agencies where required. Vessel occlusion related to the insertion or presence of a central venous catheter may be excluded from this criterion after review of the AE with the respective investigator to assess causality and/or clinical significance.
- All treatment emergent adverse events, regardless of system organ class, severity/grade, causality, and/or attribution to treatment with PF-06741086 are assessed and it is determined by the Sponsor that the limit of safety and/or tolerability has been reached.
- Dose escalation will be paused for any treatment emergent serious adverse event (SAE) that occurs in a subject receiving PF-06741086 until causality is fully assessed by the Sponsor. Dose escalation will cease if the SAE is determined to be either drug-related or unknown, and may resume if the SAE is determined to be not drug-related by the Sponsor.

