### **Dose Modifications**

Any subject who experiences a dose limiting toxicity (per [Appendix 2](#)) will be discontinued from treatment with the investigational product and will be followed for adverse event monitoring until resolution of the respective toxicity and elimination of study drug or the end of the study (Day 113) and resolution or stabilization of the respective toxicity, whichever occurs first. In addition, subjects who have not experienced dose limiting toxicities but are currently receiving a dose that met the dose limiting toxicities criteria for termination of dose escalation as defined in [Section 3.3](#) will be removed from the current dose level and dropped to the next lowest exposure level.

Subjects who have not experienced a dose-limiting toxicity may also require dose modifications. Criteria for modifications of dosing in an individual subject are as follows:

- Moderate severity infusion/injection site reactions at more than 2 consecutive visits (eg, Day 22, Day 29, and Day 36);
- Treatment emergent adverse event(s) that increases in severity/grade, without resolution, (eg, Mild to Moderate and continuing) after repeat administration of PF-06741086;

- Treatment emergent adverse event(s) of any severity with more than 2 occurrences following repeat administration of PF-06741086.

Any subject who meets the above criteria during treatment with PF-06741086 will be removed from the current dose level and dropped to the next lowest exposure level, unless the event(s) are incontrovertibly due to extraneous causes or are incontrovertibly complications of hemophilia (see [Section 8.6](#) for qualifying events).

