#### **4.2. Exclusion Criteria**

Subjects with any of the following characteristics/conditions will not be included in the study:

1. Females.
2. Known coronary artery, thrombotic, or ischemic disease.
3. Known hemostatic defect other than hemophilia A or B.
4. ATIII, Protein C, or Protein S deficiency, Factor V Leiden, Prothrombin 20210 mutation, or other known pro-thrombotic condition
5. Currently receiving treatment for acute bleeding episodes with APCC (eg, Factor Eight Inhibitor Bypass Agent [FEIBA]) and cannot substitute treatment with rFVIIa at a dose level of approximately 90 µg/kg for the duration of the study.
6. Regular, concomitant therapy with immunomodulating drugs (eg, intravenous immunoglobulin [IVIG], and routine systemic corticosteroids).
7. Abnormal renal or hepatic function as defined by the following laboratory results at Screening:
  - Alanine aminotransferase (ALT) and aspartate aminotransferase (AST) levels >3 times the upper limit of normal (ULN).
  - Total bilirubin level >2 mg/dL (>35 µmol/L).
  - Serum albumin < the lower limit of normal (LLN).
  - Serum creatinine level >1.25 times the ULN.

8. Abnormal hematology values as defined by the following laboratory results at Screening:
  - Platelet count <100,000/ $\mu$ L.
  - Fibrinogen level < LLN.
  - Hemoglobin level <10 gm/dL.
9. Abnormal coagulation activity as defined by the following laboratory results at Screening:
  - Prothrombin time (PT) >1.25 times the ULN.
10. CD4 cell count  $\leq$ 200/ $\mu$ L.
11. Known hypersensitivity or allergic reaction to hamster protein.
12. Known sensitivity to heparin or heparin-induced thrombocytopenia.
13. Investigational site staff members directly involved in the conduct of the study and their family members, site staff members otherwise supervised by the investigator, or subjects who are Pfizer employees directly involved in the conduct of the study.
14. Participation in other studies involving investigational drug(s) within 30 days (or as determined by the local requirement, whichever is longer) or 5 half-lives prior to study entry and/or during study participation.
15. Other severe acute or chronic medical or psychiatric condition or laboratory abnormality that may increase the risk associated with study participation or investigational product administration or may interfere with the interpretation of study results and, in the judgment of the investigator, would make the subject inappropriate for entry into this study.

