## Appendix 2. Criteria for Dose Limiting Toxicity

### Adverse Events

Unless incontrovertibly due to extraneous causes, treatment emergent events conforming to the following criteria will constitute dose limiting toxicity:

1. Laboratory, vital sign or electrocardiogram findings conforming to the criteria provided below;
2. When not covered by the criteria listed below, treatment emergent adverse event graded as severe or  $\geq$  Grade 3 under the NIAID Division of Microbiology and Infectious Diseases Adult Toxicity Tables (2007 Draft Version).

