### Hematology

Hemoglobin	<0.8 times the LLN or <80% times the baseline value if the baseline result is less than the lower limit of the reference range
Hematocrit	<0.8 times the LLN or <80% times the baseline value if the baseline result is less than the lower limit of the reference range
Platelets	<100,000 or $\leq$ 0.77 times the baseline value if the baseline result is less than the lower limit of the reference range.

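### Protocol Section 7.8 orders prompt recall and a repeat platelet count only below 75,000/µL, although Appendix 2 already makes a count below 100,000 a dose-limiting toxicity

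*Protocol*

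**What the plan says.** - **Recall rule (Protocol 7.8).** A subject with platelets below 75,000/µL, fibrinogen below the LLN, hemoglobin below 10 g/dL, or PT/INR at or above 1.25 times the upper limit of normal (ULN) "should be brought into the clinic immediately for an unscheduled visit and the respective laboratory test should be repeated".
- **DLT rule (Protocol Appendix 2).** The platelet limit is below 100,000, or at most "0.77 times the baseline value if the baseline result is less than the lower limit of the reference range". The general condition is: "Unless incontrovertibly due to extraneous causes, treatment emergent events conforming to the following criteria will constitute dose limiting toxicity".
- **Consequence for the subject (Protocol 3.3, Dose Modifications).** A subject with a DLT "will be discontinued from treatment with the investigational product and will be followed for adverse event monitoring until resolution of the respective toxicity". The alternative end point for this follow-up is Day 113 with the toxicity resolved or stable. No interval to a repeat test is given.
- **Consequence for the cohort (Protocol 3.3).** "Dose escalation will not occur if 2 or more dose-limiting toxicities are met within a dosing cohort of 6 subjects".
- **Entry limits (Protocol 4.2).** Exclusions at Screening include "Platelet count <100,000" per µL and "Hemoglobin level <10 gm/dL".
- **Unscheduled laboratory tests (Protocol 7.1.1).** These are permitted for safety concerns but not required.

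**The concern.** A DLT is the protocol's strongest laboratory signal, so one would expect it to bring the subject back at least as fast as a milder finding. For platelets the order is reversed: the DLT limit is crossed first, and the recall limit only after a further fall of 25,000/µL.

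Platelets are also the only row in Section 7.8 that departs from the Section 4.2 entry limit. The hemoglobin and fibrinogen limits are the same in both places, and PT differs only in whether exactly 1.25 times the ULN is included. The protocol gives no reason for 75,000.

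Two things are at stake. The first is safety: a prompt repeat shows whether the fall is real and continuing, in a trial that names platelet count as a coagulopathy parameter and thrombosis as a potential risk (Protocol 1.3.2). The second is the quality of the DLT call. A single unconfirmed count can end a subject's treatment and supply one of the two DLTs that block escalation. A repeat informs the judgement on extraneous causes and the Sponsor's review.

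**Working it through.** The plan has no figure to reproduce. The check sets the limits side by side and reads the time between scheduled hematology draws. Appendix 2 gives the platelet limit without units; I read it as per µL, as elsewhere in the protocol.

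**1. Recall limit against DLT limit**

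| Test | Recall (7.8) | Entry exclusion (4.2) | DLT (Appendix 2) |
|---|---|---|---|
| Platelets | <75,000 | <100,000 | <100,000, or ≤0.77 × baseline if baseline <LLN |
| Fibrinogen | <LLN | <LLN | ≤0.5 × LLN or ≤0.5 × baseline |
| Hemoglobin | <10 g/dL | <10 g/dL | <0.8 × LLN, or <80% of baseline if baseline <LLN |
| PT | ≥1.25 × ULN | >1.25 × ULN | ≥4 seconds above baseline |

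For a normal baseline, a platelet DLT below 100,000 against recall below 75,000 leaves 75,000 to 99,999/µL as a DLT without a recall trigger. Fibrinogen runs the other way on its LLN limb: recall comes at the LLN and the DLT at half of it. (On the baseline limb this fails only if baseline is above 2 × LLN, because half of baseline then exceeds the LLN.)

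**2. Baseline below the LLN**

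The wording of Appendix 2 leaves open whether the 0.77 clause replaces the 100,000 limit or adds to it. If it replaces it:

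- Lowest eligible Screening count: 0.77 × 100,000 = 77,000, still above 75,000.
- The DLT limit falls below 75,000 only for a baseline under 75,000 / 0.77 = 97,403.
- Baseline 110,000: limit 0.77 × 110,000 = 84,700.

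Under either reading, the 0.77 limit exceeds 100,000 once a below-LLN baseline is above 100,000 / 0.77 = 129,870. The documents do not give the LLN. If it is at most 129,870 this cannot occur. If it is 150,000 (an assumption), a baseline of 140,000 gives 0.77 × 140,000 = 107,800, so a count of 105,000 is a DLT.

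**3. Time between scheduled hematology draws (Protocol Tables 1 and 2)**

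The Table 2 windows are headed "Visit Window relative to end of Day 29 IP administration", so Day 29 is the anchor for later visits.

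| Interval | Nominal (days) | With windows (days) |
|---|---|---|
| Day 8 to 15 | 7 | at most (15+2) − (8−1) = 10 |
| Day 15 to 22, Day 22 to 29 | 7 | at most (22+2) − (15−2) = 11 |
| Day 29 to 57 | 28 | 28 ± 2 = 26 to 30 |
| Day 57 to 85 | 28 | (85−2) − (57+2) = 24 to (85+2) − (57−2) = 32 |
| Day 85 to 113 | 28 | (113−7) − (85+2) = 19 to (113+7) − (85−2) = 37 |

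The Day 30 and 33 draws and the SC-only weekly visits include no hematology. The last interval follows the end of dosing (last SC dose Day 78, last IV dose Day 57).

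**The case against.** The strongest reply is that the protocol already acts on such a count, and more forcefully than by a recall. The drug stops. Follow-up runs to resolution, which for a low count can only be shown by another count. Under Section 8.5 a result that leads to discontinuation is reportable as an adverse event, and Section 8.1 then obliges the investigator to obtain enough information on outcome and causality. Section 3.3 suspends dosing if stopping rules may have been met during cohort enrollment. All of this stands, and two stronger readings that a reader might infer fail because of it:

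- *That a count of 75,000 to 99,999/µL has no consequence or is never repeated.* It has both subject-level and cohort-level consequences, and a repeat is implied. Only promptness is missing.
- *That the subject waits 19 to 37 days for the next count.* Those are intervals between routine draws. They show that the schedule supplies no prompt count, not what a site following Sections 3.3, 8.1 and 8.5 would do. Progression also needs data at least through Day 29, and up to then the interval is at most 11 days.

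A further reply is that Section 7.8 is not a table for confirming DLTs: bilirubin, creatinine, creatine kinase and cardiac troponin I are DLT criteria without a recall row. Hemoglobin could show a similar gap if the LLN exceeds 10 / 0.8 = 12.5 g/dL, which the documents do not state. It is fair that the two lists were not built to match. It does not explain why a test that is in the recall table should have a limit laxer than both its DLT limit and its entry limit.

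The evidence for harm is also thin. The effects that lasted more than 7 days after a single 300 mg SC dose (Section 1.3.1.3) are on coagulation markers, not platelets, and the toxicology summary (Section 1.2.2) names no platelet change. Appendix 2 has no confirm-on-repeat rule, so a repeat only informs the narrow exemption for extraneous causes or exposes a laboratory error. This limits the weight of the point but does not remove it.

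**Conclusion.** The point holds as a limited gap in safety monitoring. From a normal baseline, a count of 75,000 to 99,999/µL is a DLT for which no section requires prompt recall or a prompt repeat. A later repeat is implied, with its timing unspecified, and after Day 29 routine hematology is nominally 28 days apart.

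The harm is modest: drug is stopped in any case, and no estimate, sample size or error rate is affected. The normal-baseline band rests only on the two stated limits. Statements about below-LLN baselines depend on an LLN that the documents do not give and on how the 0.77 clause is read.

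**What to change.** In Protocol Section 7.8, change the platelet trigger to: below 100,000/µL, or any count meeting the Appendix 2 platelet criterion. Leave the DLT limits and the discontinuation rule unchanged.

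The second limb is needed because 100,000 alone does not fully match Appendix 2. In the example above, the count of 105,000 from a baseline of 140,000 would be a DLT but would not be recalled.

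The cost is one table row, a few unscheduled visits, and 3 mL hematology draws (Protocol Table 6) that Section 7.1.1 already permits. Some recalls will concern subjects with a below-LLN baseline whose count may not be a DLT. For example, a count of 95,000 from a baseline of 110,000 would be recalled although it lies above the limit of 84,700, if the 0.77 clause replaces the 100,000 limit. That is an acceptable price for a prompt check.

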## **8. ADVERSE EVENT REPORTING**

### **8.1. Adverse Events**

All observed or volunteered AEs regardless of treatment group or suspected causal relationship to the investigational product(s) will be reported as described in the following sections.

For all AEs, the investigator must pursue and obtain information adequate both to determine the outcome of the AE and to assess whether it meets the criteria for classification as a serious adverse event (SAE) requiring immediate notification to Pfizer or its designated representative. For all AEs, sufficient information should be obtained by the investigator to determine the causality of the AE. The investigator is required to assess causality. Follow-up by the investigator may be required until the event or its sequelae resolve or stabilize at a level acceptable to the investigator, and Pfizer concurs with that assessment.

As part of ongoing safety reviews conducted by the Sponsor, any nonserious AE that is determined by the Sponsor to be serious will be reported by the Sponsor as an SAE. To assist in the determination of case seriousness, further information may be requested from the investigator to provide clarity and understanding of the event in the context of the clinical study.

